10.5.2. Definition of SAE

An SAE is defined as any untoward medical occurrence that, at any dose, meets one or more of the criteria listed:

- a. Results in death
- b. Is life threatening

The term *life threatening* in the definition of *serious* refers to an event in which the participant was at risk of death at the time of the event. It does not refer to an event, which hypothetically might have caused death, if it were more severe.

- c. Requires inpatient hospitalization or prolongation of existing hospitalization

- In general, hospitalization signifies that the participant has been admitted (usually involving at least an overnight stay) at the hospital or emergency ward for observation and/or treatment that would not have been appropriate in the physician's office or outpatient setting. Complications that occur during hospitalization are AEs. If a complication prolongs hospitalization or fulfills any other serious criteria, the event is serious. When in doubt as to whether hospitalization occurred or was necessary, the AE should be considered serious.
- Hospitalization for elective treatment or a pre-existing condition that did not worsen from baseline are not considered an SAE.

- d. Results in persistent or significant disability/incapacity
 - The term disability means a substantial disruption of a person's ability to conduct normal life functions.
 - This definition is not intended to include experiences of relatively minor medical significance such as uncomplicated headache, nausea, vomiting, diarrhea, influenza, and accidental trauma (eg, sprained ankle) that may interfere with or prevent everyday life functions but do not constitute a substantial disruption.
- e. Is a congenital anomaly/birth defect
- f. Other situations:
 - Medical or scientific judgment should be exercised by the Investigator in deciding whether SAE reporting is appropriate in other situations such as important medical events that may not be immediately life threatening or result in death or hospitalization but may jeopardize the participant or may require medical or surgical intervention to prevent one of the other outcomes listed in the above definition. These events should usually be considered serious.
 - Examples of such events include invasive or malignant cancers, intensive treatment in an emergency room or at home for allergic bronchospasm, blood dyscrasias, convulsions not resulting in hospitalization, or development of intervention dependency or intervention abuse.

10.5.3. Recording and Follow-Up of AE and/or SAE

AE and SAE Recording

- When an AE/SAE occurs, it is the responsibility of the Investigator to review all documentation (eg, hospital progress notes, laboratory reports, and diagnostics reports) related to the event.
- The Investigator will then record all relevant AE/SAE information.
- The Investigator will attempt to establish a diagnosis of the event based on signs, symptoms, and/or other clinical information. Whenever possible, the diagnosis (not the individual signs/symptoms) will be documented as the AE/SAE.

Assessment of Intensity

The Investigator will make an assessment of intensity for each AE and SAE reported during the study and assign it to one of the following categories:

- Mild:
A type of AE that is usually transient and may require only minimal treatment or therapeutic intervention. The event does not generally interfere with usual activities of daily living.
- Moderate:
A type of AE that is usually alleviated with additional specific therapeutic intervention. The event interferes with usual activities of daily living, causing

discomfort but poses no significant or permanent risk of harm to the research participant.

- Severe:
A type of AE that interrupts usual activities of daily living, or significantly affects clinical status, or may require intensive therapeutic intervention.

Assessment of Causality

- The Investigator is obligated to assess the relationship between study intervention and each occurrence of each AE/SAE. The Investigator will use clinical judgment to determine the relationship.
- A *reasonable possibility* of a relationship conveys that there are facts, evidence, and/or arguments to suggest a causal relationship, rather than a relationship cannot be ruled out.
- Alternative causes, such as underlying disease(s), concomitant therapy, and other risk factors, as well as the temporal relationship of the event to study intervention administration, will be considered and investigated.
- For causality assessment, the Investigator will also consult the IB and/or product information, for marketed products.
- The Investigator must review and provide an assessment of causality for each AE/SAE and document this in the medical notes. There may be situations in which an SAE has occurred, and the Investigator has minimal information to include in the initial report to SAE contact. However, it is very important that the Investigator always make an assessment of causality for every event before the initial transmission of the SAE data to SAE contact.
- The Investigator may change their opinion of causality in light of follow-up information and send an SAE follow-up report with the updated causality assessment.
- The causality assessment is one of the criteria used when determining regulatory reporting requirements.

Follow-up of AEs and SAEs

- The Investigator is obligated to perform or arrange for the conduct of supplemental measurements and/or evaluations as medically indicated or as requested by SAE contact to elucidate the nature and/or causality of the AE or SAE as fully as possible. This may include additional laboratory tests or investigations, histopathological examinations, or consultation with other health care professionals.
- If a participant dies during participation in the study or during a recognized follow-up period, the Investigator will provide SAE contact with a copy of any postmortem findings including histopathology.
- New or updated information will be recorded in the originally submitted documents.
- The Investigator will submit any updated SAE data to SAE contact within 24 hours of receipt of the information.

10.5.4. Reporting of SAEs

SAE Reporting to SAE Contact Via an Electronic Data Collection Tool

- If the electronic system is unavailable, then the site will use the paper SAE data collection tool (see next Section) to report the event within 24 hours.
- The site will enter the SAE data into the electronic system as soon as it becomes available.
- After the study is completed at a given site, the electronic data collection tool will be taken offline to prevent the entry of new data or changes to existing data.
- If a site receives a report of a new SAE from a study participant or receives updated data on a previously reported SAE after the electronic data collection tool has been taken offline, then the site can report this information on a paper SAE form (see next Section) or to the SAE contact by telephone.
- Contacts for SAE reporting will be provided by the Sponsor.

SAE Reporting to SAE Contact Via Paper Data Collection Tool

The necessity and time requirements for reporting of SAEs to the Sponsor or its designee and/or regulatory agencies are as follows:

- All SAEs will be reported by email to the SAE contact on the Study Contact Information page ([Section 10.1.1](#)) of this protocol or by fax to the number in the Investigator Site File without undue delay but not later than 24 hours after obtaining knowledge of the events, regardless of causal relationship.
- A completed SAE Report Form containing a detailed written description of the event along with available supporting documents (eg, discharge summary, autopsy report, diagnostic test results) will be provided by email to the SAE contact on the Study Contact Information page ([Section 10.1.1](#)) or by fax to the number in the Investigator Site File.
- Additional information that is not available at the time the initial SAE Report Form was completed will be promptly reviewed and provided by email to the SAE contact on the Study Contact Information page ([Section 10.1.1](#)) or by fax to the number in the Investigator Site File within 48 hours of receipt. Full supporting documentation should be solicited by the investigative site even if the SAE occurred at another institution. Such documentation may include copies of relevant subject/hospital records, discharge summaries, laboratory/test results, or autopsy reports.
- In rare circumstances and in the absence of facsimile equipment, notification by telephone is acceptable with a copy of the SAE data collection tool sent by overnight mail or courier service. Initial notification via telephone does not replace the need for the Investigator to complete and sign the SAE data collection tool within the designated reporting timeframes.
- If at any time after the subject has completed participation in the study, the Investigator or study staff becomes aware of an SAE that they suspect is related to the study medication, the event and any known details will be reported promptly by email

to the SAE contact on the Study Contact Information page ([Section 10.1.1](#)) or by fax to the number in the Investigator Site File, following the reporting instructions in this section.

10.6. Appendix 6: Concomitant Medication Considerations

A. While Taking Study Intervention (Starting from Day 1 to Week 24)

1. Prohibited Medications While Taking Study Intervention (Starting from Day 1 to Week 24)
 - Inhibitors of the RAAS.
 - Examples include (not all inclusive) the following: ACEIs, aldosterone blockers, ARBs, ERAs and aliskiren.
 - Inhibitors of the endothelin system (eg, bosentan, macitentan, and ambrisentan).
 - Potassium sparing diuretics (eg, amiloride and triamterene).
 - Thiazolidinediones should be avoided completely. Other anti-diabetic drugs (eg, metformin and glyburide) should be used in accordance with their guidelines for use in patients with impaired kidney function.
 - Digoxin, amiodarone, or any other antiarrhythmic medications that may put the patient at higher risk due to the underlying disease.
 - St. John's Wort or other hypericum-derived products.
 - Strong Cytochrome P450 3A (CYP3A) inhibitors. For a detailed list of these medications, see the P450 Drug Interaction table at:
<http://medicine.iupui.edu/clinpharm/ddis/maintable>.
NOTE: The Sponsor recognizes that, in some cases, concomitant use of these medications may be medically necessary (eg, azole antifungals for severe mycotic infections), and alternatives are either unavailable or inappropriate from a medical and safety perspective. In these cases, limited systemic exposure may be warranted; however, systemic use of strong CYP3A4 inhibitors should be avoided. In addition, a reduction in dose or temporary cessation of study intervention and more intensive patient monitoring is recommended.
- The following medications are prohibited for 7 days prior to study visits and should be used with caution at other times during the study. Investigators must review each participant case individually and use clinical judgment.
 - Sulfamethoxazole/trimethoprim (eg, Bactrim™ and Septra®), cimetidine, pyrimethamine, cetirizine, cobicistat, probenecid, vandetanib, dolutegravir, ranolazine, dronedarone, ritonavir, and telaprevir cannot be used within at least 7 days prior to any visit at which eGFR is assessed.
 - Fibrates.
2. Medications to be Used with Caution While Taking Study Intervention (Starting from Day 1 to Week 24)

It is recommended that high dose systemic corticosteroid (defined as >10 mg/day prednisone or equivalent) and/or systemic immunosuppressive therapy for the treatment of IgAN be avoided for the duration of participation in the study. If, in the Investigator's opinion, high dose systemic corticosteroid and/or systemic immunosuppressive therapy is warranted, such

intervention may be provided in addition to study intervention at the discretion of the Investigator. Consultation with the Medical Monitor is recommended before starting interventional therapy, when possible.

Similarly, it is recommended to avoid the introduction or change dose of patients receiving low dose systemic corticosteroids (defined as ≤ 10 mg/day prednisone or equivalent), enteric budesonide and/or mineralocorticoid receptor antagonists (eg. spironolactone, eplerenone, finerenone) for the duration of the study, unless, in the Investigator's opinion, such introduction is warranted, and may be provided in addition to study intervention. Appropriate potassium monitoring should be conducted for patients receiving mineralocorticoid receptor antagonists.

Consultation with the Medical Monitor is recommended before changing/starting interventional therapy, when possible.

The medications in the categories below should be avoided or used with caution while taking study intervention.

- Strong P-glycoprotein (P-gp) inhibitors.
 - In a clinical drug-drug interaction study, administration of cyclosporine increased sparsentan overall exposure by approximately 1.7-fold. Adjustment of study intervention dosage may be needed during concomitant administration of a strong P-gp inhibitor.
 - The Investigator should actively look for potential AEs, such as hypotension, hyperkalemia, or decline in eGFR during the concomitant use of a strong P-gp inhibitor. See sparsentan dose reduction guidance in [Section 6.6](#).
 - Examples relevant to the study population include (not all inclusive) the following: cyclosporine A, verapamil, and quinidine.
- CYP2B6 substrates.
 - In a clinical drug-drug interaction study, administration of sparsentan for several days decreased the exposure of bupropion, a CYP2B6 substrate, to approximately 66% to 68%.
 - Effectiveness of drugs that are CYP2B6 substrates may be reduced, and monitoring of the effectiveness of CYP2B6 substrate medications, if possible, is recommended during treatment with study intervention.
 - Examples relevant to the study population include (not all inclusive) the following: bupropion, cyclophosphamide, ketamine, meperidine, and methadone.
- NSAIDs.
 - NSAID use is discouraged during the study. Short-term (< 1 week) or intermittent NSAID, including aspirin use, is allowed. Chronic low dose aspirin at doses ≤ 100 mg/day for cardiovascular protection is allowed during the study.
- Lithium.
 - Caution is required when combining lithium with inhibitors of RAAS as it may enhance the actions of ACEIs or ARBs.

- Warfarin.
 - Although no specific drug-drug interaction clinical studies have been performed, a theoretical potential exists for a drug-drug interaction between sparsentan and warfarin via protein binding displacement.
 - International normalized ratio (INR) monitoring is recommended if warfarin is used concomitantly with study intervention.

3. Additional Information

Additional medications potentially interacting with sparsentan (CYP3A inhibitors, P gp inhibitors, and CYP 2B6 substrates) can be found at:

[http://medicine.iupui.edu/clinpharm/ddis/main table/](http://medicine.iupui.edu/clinpharm/ddis/main_table/)

B. Prohibited Medications Following Discontinuation of Study Intervention (ie, Non-Treatment Period from Week 24 to Week 28)

- Thiazolidinediones should be avoided completely. Other anti-diabetic drugs (eg, metformin and glyburide) should be used in accordance with their guidelines for use in patients with impaired kidney function.
- Digoxin, amiodarone, or any other antiarrhythmic medications that may put the patient at higher risk due to the underlying disease.
- Amphetamines and amphetamine derivative agents.
- The following medications are prohibited for 7 days prior to study visits and should be used with caution at other times during the study. Investigators must review each patient case individually and use clinical judgment.
 - Sulfamethoxazole/trimethoprim (eg, Bactrim™ and Septra®), cimetidine, pyrimethamine, cetirizine, cobicistat, probenecid, vandetanib, dolutegravir, ranolazine, dronedarone, ritonavir, and telaprevir cannot be used within at least 7 days prior to any visit at which eGFR is assessed.
 - Fibrates.

C. Participants Who Have Permanently Discontinued Study Intervention Prior to Safety Follow-Up Visit

- The following medications are prohibited for 7 days prior to study visits and should be used with caution at other times during the study. Investigators must review each patient case individually and use clinical judgment.
 - Sulfamethoxazole/trimethoprim (eg, Bactrim™ and Septra®), cimetidine, pyrimethamine, cetirizine, cobicistat, probenecid, vandetanib, dolutegravir, ranolazine, dronedarone, ritonavir, and telaprevir cannot be used within at least 7 days prior to any visit at which eGFR is assessed.
 - Fibrates.

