6. Participant has been on a stable dose of ACEI and/or ARB therapy for at least 12 weeks prior to screening that is:
 - a. The participant's maximum tolerated dose (MTD), and
 - b. at least one half of the maximum labeled dose (MLD) (See [Section 10.2](#) for minimum ACEI/ARB daily dose requirements at screening).
7. The participant has been on a stable dose of an SGLT2 inhibitor for at least 12 weeks prior to screening.
8. Participant systolic BP must be ≤ 160 mmHg, and diastolic BP must be ≤ 110 mmHg at screening.
9. For participants receiving chronic low dose systemic corticosteroids (defined as ≤ 10 mg/day prednisone or equivalent), or an enteric formulation of budesonide and/or a mineralocorticoid receptor antagonist (MRA), the dosage must be stable for ≥ 12 weeks prior to screening.
10. The participant is willing to undergo a change in ACEI and/or ARB and anti hypertensive medications.

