5.2. Exclusion Criteria

Participants are excluded from the study if any of the following criteria apply:

Medical Conditions

1. Participant has IgAN secondary to another condition (eg, systemic lupus erythematosus and liver cirrhosis) or immunoglobulin A (IgA) vasculitis.
2. Participant has undergone any organ transplantation, with the exception of corneal transplants.
3. Participant has a documented history of heart failure [New York Heart Association (NYHA) Class II-IV] and/or previous hospitalization for heart failure or unexplained dyspnea, orthopnea, paroxysmal nocturnal dyspnea, ascites, and/or peripheral edema (see [Section 10.4](#) for assessment of peripheral edema).

4. Participant has clinically significant cerebrovascular disease (transient ischemic attack or stroke) and/or coronary artery disease (hospitalization for myocardial infarction or unstable angina, new onset of angina with positive functional tests, coronary angiogram revealing stenosis, or a coronary revascularization procedure) within 3 months prior to screening.
5. Participant has jaundice, hepatitis, or known hepatobiliary disease (excluding asymptomatic cholelithiasis), or ALT and/or AST >2 times the ULN range at screening.
6. Participant has a history of malignancy other than adequately treated basal cell or squamous cell skin cancer or cervical carcinoma within the past 2 years.
7. Participant has a history of serious side effect or allergic response to any AngII antagonist, ERA or sparsentan, or has a hypersensitivity to any of the excipients in the study intervention.

Prior/Concomitant Therapy

8. Participant requires any of the prohibited concomitant medications ([Section 10.6](#)).
9. Participant has been taking high dose systemic corticosteroids (defined as >10 mg/day prednisone or equivalent) or other any systemic immunosuppressive medications or enteric budesonide greater than the MLD and/or a MRA greater than the MLD within 12 week prior to screening.

Prior/Concurrent Clinical Study Experience

10. Treatment with sparsentan within 12 weeks prior to screening
11. Participant has participated in a study of another investigational product within 28 days prior to screening or plans to participate in such a study during the course of this study.

Diagnostic Assessments

12. Participant has a screening hematocrit value <27% (0.27 Volume/Volume) or hemoglobin value <9 g/dL (90 g/L).
13. Participant has a screening potassium value of >5.5 mEq/L (5.5 mmol/L).

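### Appendix 6 of the protocol prohibits aldosterone blockers on treatment, yet for the same 24 weeks it lets MRAs be given with sparsentan; through Exclusion 8 the prohibition also contradicts Inclusion 9

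*Protocol*

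**What the plan says.** **Appendix 6, A.1.** The heading reads "Prohibited Medications While Taking Study Intervention (Starting from Day 1 to Week 24". Under the RAAS-inhibitor bullet it states: "Examples include (not all inclusive) the following: ACEIs, aldosterone blockers, ARBs, ERAs and aliskiren". That bullet has no exception. The one medical-necessity note in A.1 belongs to strong CYP3A inhibitors. A separate A.1 bullet prohibits potassium-sparing diuretics, with amiloride and triamterene as examples.

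**Appendix 6, A.2.** The heading reads "Medications to be Used with Caution While Taking Study Intervention (Starting from Day 1 to Week 24", which is the same period. The text advises against starting or changing the dose of "mineralocorticoid receptor antagonists (eg. spironolactone, eplerenone, finerenone) for the duration of the study", unless the investigator judges that "such introduction is warranted, and may be provided in addition to study intervention". It recommends consulting the Medical Monitor before starting or changing therapy, and adds: "Appropriate potassium monitoring should be conducted for patients receiving mineralocorticoid receptor antagonists".

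**Eligibility (Sections 5.1 and 5.2).** Inclusion 9 covers participants on low-dose steroids "or an enteric formulation of budesonide and/or a mineralocorticoid receptor antagonist (MRA), the dosage must be stable for" at least 12 weeks before screening. Exclusion 9 bars "enteric budesonide greater than the MLD and/or a MRA greater than the MLD within 12 week prior to screening", so an MRA at or below the maximum labeled dose (MLD) is not a ground for exclusion there. Exclusion 8 bars anyone who requires a drug prohibited in Section 10.6. Section 5 allows no waivers of enrollment criteria.

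**Elsewhere.** Section 6.6 names ACEIs, aliskiren, ARBs and ERAs as the antihypertensives that may not be added, refers to Section 10.6, and does not name aldosterone blockers. The Synopsis (Study Arms and Duration) has prohibited medications stopped before the Day 1 visit. Section 4.1 fixes the last ACEI/ARB dose to the day before Day 1; no such rule exists for an MRA.

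**The concern.** One class of drug appears under both the prohibited and the use-with-caution headings for the same treatment period, and no rule says which governs. A site that follows A.1 would turn away, or take off their MRA, participants whom the eligibility criteria are written to admit. A site that follows A.2 would enroll them and leave the MRA in place.

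Three things are at stake:

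- **Eligibility.** A participant who requires a stable MRA at or below the MLD satisfies Inclusion 9 and Exclusion 9 but fails Exclusion 8 through A.1.
- **The primary endpoint.** The study has one arm and measures UA/C change from Day 1 to Week 24. If an MRA is stopped around baseline, the change for that participant mixes MRA withdrawal with the sparsentan effect, and no control group separates them. The intercurrent events in SAP 8.2.1 do not include a change in MRA.
- **The per-protocol set.** SAP 7.3 makes freedom from prohibited medication a condition of evaluability. Whether an MRA user belongs in the set therefore depends on which part of Appendix 6 is read.

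**Working it through.** No figure in the plan bears on this point. The check is a comparison of texts.

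**Step 1: same drugs?** The protocol does not define aldosterone blockers. I take the term in its ordinary sense, which covers the MRAs that A.2 names (spironolactone, eplerenone, finerenone). Nothing in A.1 carves them out.

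**Step 2: same period?** Yes. Both headings run from Day 1 to Week 24, so the overlap is the whole treatment period.

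**Step 3: which text is probably wrong?**

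| Place | What it implies for MRAs |
|---|---|
| Appendix 6 A.1 | Prohibited |
| Appendix 6 A.2 | Cautious use; introduction allowed if judged warranted; potassium monitored |
| Inclusion 9 | Users are expected at entry, on a stable dose |
| Exclusion 9 | Only doses above the MLD are barred |
| Section 6.6 | Not named among the barred antihypertensives |

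Inclusion 9 and Exclusion 9 are screening rules and do not in themselves authorize use on treatment. They do show that MRA users are meant to be enrolled. A.2 goes further, because advice on dose changes and on monitoring patients who receive an MRA presupposes that some participants are still taking one. Four places lean one way against one entry in a list of examples, so the A.1 entry is probably the mistake.

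**Step 4: what follows if A.1 is applied literally?**

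- *The participant requires the MRA.* Exclusion 8 applies, Inclusion 9 is defeated, and Section 5 rules out a waiver.
- *The participant can do without it.* The Synopsis has it stopped before Day 1, on no stated day. SAP 6.4.2 takes baseline UA/C from two first-morning samples within 3 days before Day 1. Depending on the stop day, those samples may be taken on the MRA or some time after it, while the Week 24 samples are taken off it. What the change measures can then differ from one participant to the next.

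**Step 5: can the effect be sized?** No. The documents give neither the expected number of MRA users among the approximately 60 participants nor the effect of MRA withdrawal on UA/C. Counting days off the drug would describe the calendar and not a bias.

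**The case against.** The strongest reply is that sites have enough to work out the intended meaning. A.2 names the individual drugs, three other places agree with it, and Section 6.8 sends questions about concomitant therapy to the Medical Monitor. Section 6.8.1 also softens A.1: a participant with a clinical indication for a prohibited drug may stay on sparsentan if investigator, sponsor and participant agree. A reader might infer that A.1 is an absolute bar on treatment, and Section 6.8.1 shows that it is not.

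This reduces the practical harm but does not remove the conflict. Section 6.8.1 works case by case for people already on treatment; it does not reconcile Exclusion 8 with Inclusion 9. The Medical Monitor helps only if a site asks, and a site that reads A.1 alone sees nothing to ask about.

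A second reply concerns potassium. A reader might infer that the conflict leaves hyperkalemia uncontrolled. It does not. Exclusion 13 bars potassium above 5.5 mEq/L at screening, and Appendix 8 checks potassium at each visit, with steps up to permanent discontinuation. Both apply whichever part of Appendix 6 a site follows. What differs between sites is only whether an MRA is combined with sparsentan.

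A third reply is that the study is exploratory and descriptive, with no efficacy hypothesis (Sections 9.1 and 9.3.3). The per-protocol set serves sensitivity analyses only (SAP 6.3.2) and is reviewed before database lock (SAP 7.3). This stands, and it limits the weight of the point.

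**Conclusion.** The plan is wrong as written. A.1 and A.2 give incompatible instructions for MRAs over the same period, and A.1 read with Exclusion 8 gives an eligibility answer contrary to the evident purpose of Inclusion 9. The conclusion rests on reading aldosterone blockers to include MRAs.

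A reader might infer that the primary UA/C result is biased. The documents do not support that. They show a route by which MRA withdrawal could confound the change from baseline, but only for participants whose MRA is stopped under A.1. How many there would be, and in which direction and by how much their results would shift, is unknown. The firm part is the eligibility and treatment instruction; the endpoint and per-protocol consequences are conditional on how sites read it.

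**What to change.** In Appendix 6 A.1, add one exception to **both** the RAAS-inhibitor bullet and the potassium-sparing-diuretic bullet:

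*except mineralocorticoid receptor antagonists used in accordance with Inclusion Criterion 9 and Exclusion Criterion 9, or introduced or dose-adjusted under A.2.*

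The exception has to be this wide for three reasons:

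- Deleting aldosterone blockers from the examples would not be enough, because the list is not exhaustive and the class heading would still cover MRAs.
- Exempting only MRAs stable at entry would leave introductions and dose changes under A.2 literally prohibited.
- The potassium-sparing-diuretic bullet also lists examples only. The documents do not say whether an MRA falls within it, so the exception should close that question too.

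Optionally, add a line to SAP 7.3 that MRA use permitted in this way is not a prohibited-medication deviation for the per-protocol set.

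The cost is one clause and, if wanted, one SAP line, with no new visits, procedures or data. The protocol change may need IRB/IEC approval (Section 10.1.2) across approximately 30 sites, so it can go into the next amendment. Until then the Medical Monitor should give all sites the same written clarification of the intended reading, framed as a clarification because Section 5 does not allow waivers.
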